#### ***iii) Cost-effectiveness analysis***

CEA on person-level cost and effect data will be conducted using net benefit (nb) regression described by our collaborator ([name]). This technique allows CEA to be conducted using traditional

regression methods. The dependent variable for the net benefit regression in this analysis will be  $nb$  which equals  $effect \times \$ - cost$  where  $effect =$  primary outcome of IIRS,  $\$ =$  the monetary value of each unit of effect and  $cost =$  the costs accrued over the study period. As noted above, the data for effect and for cost will be collected as part of the study's comparison of the two reconstructive methods. Different values of  $\$$  will be used to see how sensitive the results are to assumptions about  $\$$ . In the base case scenario, the dependent variable  $nb$  will be modeled as a function of an indicator variable ( $TX=0$  if in the two-stage TE/I group and  $TX=1$  if in the one-stage ADM assisted group) and potentially confounding variables. We shall estimate the coefficient  $\beta_{TX}$  in the regression  $nb = \beta_0 + \beta_x \mathbf{X} + \beta_{TX} TX + \varepsilon$  where  $\mathbf{X}$  is a vector of potentially confounding variables,  $\beta_x$  is a vector of their respective coefficient estimates,  $\varepsilon$  is a stochastic error term,  $TX$  is the new treatment indicator and  $\beta_{TX}$  is an estimate of the incremental net benefit. When  $\beta_{TX} > 0$ , the intervention is deemed to be cost-effective since the value of the extra benefit is greater than the extra cost. Net benefit regressions will be repeated for a variety of  $\$$  values and then the probability of cost-effectiveness will be plotted against values for  $\$$  on a cost-effectiveness acceptability curve. In this way, the research findings will allow different decision makers to use different preferred values of  $\$$ . By placing the CEA in a regression framework, we will then be able to use a wide variety of regression tools, for example, those to identify key subgroups for hypothesis generation and model diagnostic tools.

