### iib-3) Cost effectiveness analysis

Despite the importance of cost effectiveness analysis (CEA) in evaluating health outcomes and resource costs in surgical interventions, there is a paucity of this research in the area of post-mastectomy reconstruction. Paramount in the CEA, is not only considerations of direct and indirect cost of intervention, but also patient perception of their health outcome (utility) and complications or morbidity as a consequence of the intervention. This sister analysis can be easily added to our current ongoing RCT, since we are already prospectively collecting information on both short- and long-term complications, patient satisfaction and QOL as part of the study protocol. In addition, we will add the EQ-5D QOL instrument that addresses 5 dimensions to evaluate the health status as reported by patients at the same time-points as the Breast Q©. Cost effectiveness analysis will be performed on **person-level cost** (direct and indirect) and **effect** data (Breast Q© global score and utility value on EQ-5D) using **net benefit regression**, a novel technique developed by our collaborator.([name]) The cost data will come from hospital cost accounting systems and patient

reports. Accurate case costing information is collected by the Accounting Department of the hospitals with each patient visit to the ambulatory clinic, emergency department, operating room, or in-patient ward. The primary patient outcome measure will be the global Breast Q© score and the secondary outcome measure will be quality adjusted life years (QALY) as measured by the EQ-5D. The versatility of the net benefit regressions is that it can be modeled for a variety of monetary values with the probability of cost-effectiveness plotted against values for money on a cost-effectiveness acceptability curve. By eliminating the process of tissue expansion and a second operative procedure, we hypothesize that both the cost and utility as valued by patients will be superior in the 1-stage ADM method compared to the 2-stage TE/I method.

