#### Study Schema:

Baseline Measure	Skin-sparing or Nipple-sparing mastectomy	Outcome Measure
Stratify by:		
1. Site	Acellular dermal matrix assisted one-stage implant reconstruction	1. Breast Q ©
UHN WCH VGH		2. EQ-5D
2. Laterality		3. Complications
Unilateral Bilateral		4. Aesthetics
	Two-stage tissue expander/implant reconstruction	5. Cost-effectiveness

The **primary outcome** evaluated will be **patient-reported satisfaction and quality of life** associated with the use of ADM in one-stage immediate prosthetic breast reconstruction following skin-sparing or nipple-sparing mastectomy. Patient-reported satisfaction and quality of life will be measured using the Breast Q© questionnaire. These questionnaires will be administered to patients prior to mastectomy, at two weeks following the mastectomy and immediate reconstruction, 6 months and one year (+/- 1 month) following completion of reconstruction. It is hypothesized that ADM assisted one-stage prosthetic breast reconstruction will be associated with improvement in patient-reported satisfaction and quality of life compared to the conventional two-stage TE/implant reconstruction.

The **secondary outcomes** will include **short and long-term complication rates**, overall **aesthetic outcome** including capsular contracture formation at six month and one-year following completion of the reconstruction, and a **cost effectiveness analysis (CEA)**. For the cost-effectiveness analysis, person-level cost and effect data will be collected throughout the study. The cost data will come from hospital cost accounting systems and patient reports. The patient outcome data will be collected at months 6 and 12 months post-mastectomy by the Breast Q© and EQ-5D. The primary measure of effectiveness will be the global Breast Q© score and the secondary measure will be quality adjusted life years (QALY) as measured by the EQ-5D. It is hypothesized that the short- and long-term complication rates will be comparable between the two study arms, while the overall aesthetic outcome will be superior with less severe capsular contracture in the ADM assisted one-stage than the two-stage TE/implant reconstruction. Lastly, we hypothesize ADM assisted one-stage implant reconstruction will be the more cost effectiveness method of implant reconstruction following mastectomy than the standard two-stage TE/I method.

Timing of Questionnaires

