#### **iib-7. Confounders and their Measurements**

Critical covariates will be identified at baseline and documented in the demographic assessment forms. These confounders can be conceptually divided into procedure specific, patient specific, and disease specific confounders. Analysis will be adjusted for the confounders using both stratification and multivariate regression. (see section on Outcome and their measurements) Stratified randomization is

performed based on laterality of the reconstruction (unilateral vs. bilateral) and study site. Other procedure specific confounders include skin-sparing vs. nipple-sparing mastectomy and the primary reconstructive surgeon. The patient specific confounders will include age, body mass index; socioeconomic status assessed using proxy measures of income and highest obtained level of education and marital status. Co-morbidities will be categorized as having one or more the following possible chronic conditions (emphysema, heart disease, diabetes, hypertension, stroke, arthritis, or other chronic condition). The disease specific confounders will include stage of breast cancer and present or past chemotherapy treatment.

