2. **long-term aesthetic result**: Evaluation of the overall aesthetic result and capsular contracture grade will be performed at six months and one year following the completion of reconstruction. A routine physical examination will be performed by the attending surgeon and photographic documentation (5 standardized photographs) of the reconstruction will be obtained at the six month and one-year follow-up visit. A panel of three independent, blinded observers will subsequently evaluate the overall aesthetic result using the three-point, five item, Breast Aesthetic Score described by Lowery with the use of photographic documentation. Capsular contracture will be graded by the examining physician and will be graded using the Modified Baker Scale for Reconstructed Breasts, which is widely accepted to be the gold-standard measure of capsular contracture grade.
3. **cost-effectiveness**: Costs and effects will be simultaneously analyzed by collecting person-level cost and effect data. The cost data will come from hospital cost accounting systems and patient reports. The patient outcome data will be collected at months 6 and 12 months post-mastectomy by Breast Q $\circ$

and EQ-5D. The frequently used generic HRQoL instrument EQ-5D will be piggy-backed to the Breast QoL at the 2 post-mastectomy time-points to generate a utility value for current health. The primary measure of effectiveness will be the Breast Q score and the secondary measure will be quality adjusted life years (QALY) as measured by the EQ-5D (APPENDIX 6)

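### Baseline EQ-5D is scheduled but not pre-specified as a covariate in the QALY net-benefit regression, which gives up precision that costs nothing to recover

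*Combined protocol and SAP*

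**What the plan says.** The Study Schema section makes the Breast Q the primary effectiveness measure of the cost-effectiveness analysis and adds that "the secondary measure will be quality adjusted life years (QALY) as measured by the EQ-5D". Section 9c iii) regresses net benefit on a treatment indicator and X, which "is a vector of potentially confounding variables". It names no element of X and does not refer to a list.

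The only list of covariates is in iib-7:
- Stratification factors: laterality and site.
- Procedure: "Other procedure specific confounders include skin-sparing vs. nipple-sparing mastectomy and the primary reconstructive surgeon".
- Patient: "The patient specific confounders will include age, body mass index; socioeconomic status assessed using proxy measures of income and highest obtained level of education", with marital status and co-morbidities.
- Disease: "The disease specific confounders will include stage of breast cancer and present or past chemotherapy treatment".

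Baseline EQ-5D is not in it. Section 9a links the covariates to the demographic forms and to the repeated measures analysis and adds no others.

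The plan is not consistent on when EQ-5D is given. The timing table marks baseline, 6 and 12 months. The Innovation section on cost-effectiveness has it "as reported by patients at the same time-points as the Breast Q", which would also include 2 weeks. The Study Schema section names only 6 and 12 months for the cost-effectiveness outcome data. Section iib-8, item 3, attaches it to the Breast Q "at the 2 post-mastectomy time-points to generate a utility value for current health". No formula for turning EQ-5D values into QALYs is given.

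**The concern.** A woman's utility before surgery is likely to predict her utility afterwards. If the QALY is an area under the curve that starts at baseline, it is also a component of the outcome. An analyst who fills X from the iib-7 list would leave it out. Part of any difference between the arms that was there before surgery would then appear in the observed QALY difference and be multiplied by the dollar value per QALY, and the comparison would be noisier than it needs to be. If X is instead chosen after the data are seen, the choice of adjustment is open to influence by the result. The Breast Q primary analysis in 9c i) does bring in the pre-surgery score; the QALY analysis has no stated counterpart.

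**Working it through.** **The plan's own figure.** Section iib-10 gives 72 per arm for a 10-point Breast Q difference with SD 20, two-sided alpha 0.05 (sidedness inferred) and 85% power. Check: 2 × (1.960 + 1.036)² × (20/10)² = 71.8, so 72. It reproduces, but it concerns the Breast Q. The plan states no SD, correlation or standard error for EQ-5D, QALYs or net benefit, so what follows rests on assumptions.

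**Assumptions.** Utility has the same SD σ at 0, 6 and 12 months, with a common correlation r between any two visits. Two QALY constructions are considered:
- Trapezoid: 0.25·u0 + 0.5·u6 + 0.25·u12.
- Follow-up only: 0.5·u6 + 0.5·u12.

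**Formulas, in units of σ².** V is the variance of the QALY and C its covariance with baseline.
- Trapezoid: V = 0.375 + 0.625r and C = 0.25 + 0.75r.
- Follow-up only: V = 0.5 + 0.5r and C = r.

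Then R² = C²/V, and the adjusted standard error is √(1 − R²) times the unadjusted one. For the trapezoid at r = 0.5: V = 0.6875, C = 0.625, R² = 0.3906/0.6875 = 0.568, and √0.432 = 0.657, a cut of 34%.

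| r | Trapezoid: R² | SE cut | Unadjusted SE larger by | Follow-up only: R² | SE cut | Unadjusted SE larger by |
|---|---|---|---|---|---|---|
| 0.3 | 0.401 | 23% | 29% | 0.138 | 7% | 8% |
| 0.5 | 0.568 | 34% | 52% | 0.333 | 18% | 22% |
| 0.7 | 0.739 | 49% | 96% | 0.576 | 35% | 54% |

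**Carry-over of imbalance.** With 72 per arm the baseline difference has standard error √(2/72) = 0.167 SD, so a 95% range of ±0.33 SD. Because the baseline variance is σ², the expected carry-over per unit of baseline difference is C: 0.475/0.625/0.775 for the trapezoid and 0.3/0.5/0.7 for follow-up only. It is partial in every case.

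**Dilution in net benefit.** If a share s of the variance of net benefit comes from the QALY term and costs are independent of utility, the factor becomes √(1 − s·R²). At r = 0.5 the cut is:
- s = 0.5: 15% (trapezoid), 9% (follow-up only).
- s = 0.25: 7% (trapezoid), 4% (follow-up only).

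**Missing baselines.** The Innovation section speaks of adding EQ-5D to a running trial, and the Preliminary Data section reports 51 women already randomized. If all 51 of 144 lacked a baseline value, a fraction p = 93/144 = 0.646 would contribute. At r = 0.5:
- Follow-up only: √(1 − 0.646 × 0.333) = 0.886, a cut of 11%.
- Trapezoid, with the missing baseline term set to the overall mean: those women have QALY variance 0.25 + 0.0625 + 0.25 × 0.5 = 0.4375. The average variance is 0.646 × 0.6875 + 0.354 × 0.4375 = 0.599 unadjusted and 0.646 × 0.2969 + 0.354 × 0.4375 = 0.347 adjusted (0.2969 = 0.6875 − 0.3906). √(0.347/0.599) = 0.761, a cut of 24%.

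**The case against.** The strongest reply is that the plan does not leave baseline utility out. X is open, 9c iii) does not point to iib-7, and 9a ties the listed covariates to other analyses. That stands against the inference that the plan excludes baseline EQ-5D. It does not answer the point that the plan fails to name it.

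A second reply is that randomization makes the unadjusted estimate unbiased and that its standard error already allows for chance imbalance. This is also right. A reader might infer that baseline imbalance passes whole into the result as bias; it passes only in part, and the carry-over and the larger standard error are two views of one thing, not two separate harms.

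Third, the trapezoid figures depend on a construction that the plan does not state. Its weights also assume visits at 6 and 12 months after mastectomy, as the cost-effectiveness text has it, whereas iib-8 times the Breast Q visits from completion of reconstruction. This stands, and is why the follow-up-only figures are shown beside them.

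Fourth, listed covariates such as co-morbidity may already absorb some of the gain. That is possible, and the documents do not allow it to be sized.

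**Conclusion.** The point holds as a free improvement of minor severity. Baseline utility is on the schedule but is not pre-specified for the QALY regression, and naming it improves precision under either QALY construction at every correlation tried. The size runs from a 7% to a 49% cut in the standard error of the QALY difference, depending on an assumed correlation (0.3 to 0.7), equal SDs, complete baseline data and an unstated QALY formula.

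Two further readings are not supported. A reader might take a single figure, such as a standard error one third too large, as the size or the upper limit. The documents give no correlation to fix it, and a cut of one third is not the same as an excess of one third: at r = 0.5 the trapezoid cut of 34% means an unadjusted error 52% larger. A reader might also apply these percentages to incremental net benefit, the quantity that 9c iii) estimates. There, cost variance reduces them, by an amount the documents do not determine.

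The consequence is limited. QALY is the secondary effectiveness measure of the third secondary objective, and neither the Breast Q primary analysis nor the sample size is affected.

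**What to change.** In 9c iii), state that baseline EQ-5D utility is a pre-specified member of X in every QALY-based net-benefit regression and in the acceptability curves drawn from them. In the same edit:
- Give the QALY formula, including whether baseline enters it and from which event visit times are counted.
- Reconcile the EQ-5D time-points in the Innovation section, the Study Schema section, the timing table and iib-8, item 3.
- For women without a baseline EQ-5D, set the covariate to the overall baseline mean and add a missing indicator. If the trapezoid is used, apply the same fill to the baseline term of the QALY; otherwise those women have no computable outcome, and filling the covariate alone does not keep them in the regression.

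The cost is a few sentences of text and one covariate plus an indicator in the model. The timing table already schedules the baseline EQ-5D, so no new data collection is needed.

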### **iib-10. Sample Size**

We consider clinically relevant change in the quality of life as a difference that exceeds half a standard deviation of the baseline value. Field-testing data of the Breast Q $\odot$  has found that the standard deviation of both the psychosocial function and satisfaction distributions is approximately 20. Thus, the minimum significant difference of score in each subscale is calculated to be 10. When we set our power at 85% with a  $\beta$  error of 0.1 and a standard  $\alpha$  error rate of 0.05, and applied the equation for equal sample sizes, we calculated a **minimum sample size of 72 patients per arm** for a total sample size of 144 patients. This sample size is also sufficient with power 84%,  $\alpha$  0.05, to detect a value of 0.06 for  $\eta^2$ , representing a medium effect size of the proportion of variability in the outcome variable (Breast Q $\odot$ ) that is explained by the independent variable(s), e.g., intervention.

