1. To compare patient satisfaction and QOL between one-stage ADM and two-stage TE/I reconstruction without ADM following mastectomy. Patient satisfaction will be evaluated using the Breast Q© at two-weeks, as well as six months and one year following completion of reconstruction.

**Hypothesis:** Patient satisfaction and QOL will be higher in the ADM assisted one-stage implant reconstruction group compared to the two-stage TE/I group at all three time-points.

The **secondary objectives** of this study are:

1. To compare the short- and long-term complication rates between the two techniques.

**Hypothesis:** The use of ADM in one-stage prosthetic breast reconstruction is not associated with increased short- and long-term postoperative complications compared with the traditional two staged TE/I procedure.

2. To examine the overall aesthetic outcome achieved using the ADM facilitated one-staged breast reconstruction at six months and one year following completion of the reconstruction.

**Hypothesis:** The overall aesthetic outcome achieved using the ADM facilitated one-stage breast reconstruction is superior to that following the two-stage breast reconstruction.

3. To perform a cost-effectiveness analysis (CEA) of the two reconstruction methods using the net benefit regression model on person-level cost and effect data collected during the study.

**Hypothesis:** Both the direct and indirect cost will be reduced and patient-reported utility will be greater for the one-stage ADM method compared to the TE/I method.

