### **9c. Measurement of the Primary Objective:**

#### ***i) Primary Analysis***

Each of the two domain-specific summary scores on function and satisfaction will be transformed on a scale from 0 to 100 using RUMM software. Mean scores and standard deviation for each surgery group will be calculated and compared. To address our primary aim of comparing patient satisfaction and quality of life between **Group 1** (one-stage with ADM) and **Group 2** (two-stage group without ADM) before and at the three post mastectomy follow up reference time points, we will use the **repeated measure analysis** to examine the time effect and time-group interaction. In all analyses, statistical significance will be designated at  $p <= 0.05$  level.

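### The sample-size section pairs 85% power with a beta of 0.1, and the 85% belongs to a two-group comparison that the primary analysis does not specify

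*Combined protocol and SAP*

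**What the plan says.** Section iib-10 (Sample Size) takes half a standard deviation as the relevant difference. It puts the SD at about 20 for both the psychosocial function and satisfaction scores, and so arrives at 10 points in each subscale. It continues: "When we set our power at 85% with a $\beta$ error of 0.1", with alpha 0.05 and the formula for equal groups, and obtains 72 per arm, 144 in total. Section iib-1 (Study Design) makes clear that 72 is the evaluable number. A second sentence in iib-10 begins "This sample size is also sufficient with power 84" per cent and refers to an eta-squared of 0.06 explained by, for example, the intervention.

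Section 9c i (Primary Analysis) has two subscale scores. It says: "Mean scores and standard deviation for each surgery group will be calculated and compared". It then addresses the aim of comparing the two groups "before and at the three post mastectomy follow up reference time points" by a repeated measures analysis "to examine the time effect and time-group interaction", with significance at 0.05 in all analyses.

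The primary hypothesis in section i (Specific Aims) is that satisfaction and quality of life are higher with ADM "compared to the two-stage TE/I group at all three time-points".

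**The concern.** There are two problems. The first is numerical: 85% power means a beta of 0.15, and a beta of 0.1 means 90% power. A reader cannot tell from the sentence which was meant, and the two lead to different sample sizes.

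The second has more consequence. The sample size was worked out for one comparison, the analysis section names other effects, and the hypothesis claims something else again. The time effect asks whether scores change over the study, whatever the arm. The time-group interaction does compare the arms, but it is an omnibus test, without direction, of whether they change differently. Neither is the two-group difference that was powered, and neither can show that ADM is higher at each follow-up visit. That would have to be read from group means for which no contrast is specified, on two subscales with no rule for what counts as success. The plan therefore does not say which result would confirm the primary hypothesis.

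**Working it through.** **Inputs.** From iib-10: difference 10, SD 20, alpha 0.05, equal groups, 72 per arm. The section does not say whether the test is one- or two-sided; two-sided is assumed first.

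**Reproducing 72.** n per arm = 2 × (z for alpha + z for power)² / (10/20)².
- 85% power: 2 × (1.960 + 1.036)² / 0.25 = 71.8, so 72.
- 90% power (beta 0.1): 2 × (1.960 + 1.282)² / 0.25 = 84.1, so 85.
- With the noncentral t distribution the figures are 73 and 86.
- Power at 72: the standardised difference is 0.5 / √(2/72) = 3.0, and Φ(3.0 − 1.96) = 85.1%; by t, 84.6%.
- One-sided alpha 0.05: 58 per arm for 85% power and 69 for 90%; 72 per arm gives 91%.

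The plan's 72 is matched by 85% power, two-sided, with beta 0.15. No reading satisfies both 85% and beta 0.1.

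**The eta-squared sentence.** f² = 0.06/0.94 = 0.0638, so d = 2f = 0.505, or 10.1 points at SD 20. With two groups and 144 patients, the noncentrality is 144 × 0.0638 = 9.19 and F(1,142) gives 85.3% power, against the stated 84%. Conversely, d = 0.5 corresponds to 0.25/4.25 = 0.0588. This is in effect the same group comparison.

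**Does the 85% carry over to the interaction?** With baseline and three follow-up visits, the interaction has 3 degrees of freedom. Its power depends on the correlation between visits. The documents do not give this, so the values 0.3, 0.5 and 0.7 are assumptions, with complete data. The noncentrality is (72/2) × d′(CΣC′)⁻¹d, where d holds the between-arm differences in change from baseline, C forms those changes and Σ is the covariance of the four visits. For a 10-point benefit at all three follow-up visits:

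| Assumed structure | 0.3 | 0.5 | 0.7 |
|---|---|---|---|
| Compound symmetry, F(3,426): noncentrality | 9.64 | 13.5 | 22.5 |
| Power | 74% | 88% | 99% |
| First-order autoregressive, multivariate F(3,140): noncentrality | 7.85 | 10.0 | 15.6 |
| Power | 63% | 75% | 92% |

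**Does a significant interaction show benefit at every visit?** For a 10-point benefit at 2 weeks only, power is 74/88/99% under compound symmetry and 74/90/99% under the autoregressive structure. A short-lived benefit is thus detected at least as readily as a lasting one in these scenarios, so significance does not tell the two apart.

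**Two subscales** (normal approximation, assumed correlation between subscales 0 to 0.9).
- If both must be significant: joint power 72% to 81%.
- If either suffices at 0.05 each: false-positive rate 9.8% falling to 7.0%.
- Holm, when only one subscale differs: its first step is at 0.025, and Φ(3.0 − 2.241) = 77.6%.

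**Three visits.** If significance at every visit were required on one subscale, power would be about 62% to 79% at an assumed between-visit correlation of 0 to 0.9. The plan does not state such a requirement.

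**The case against.** The best defence is that little is actually wrong with the numbers. The stated 85% is right to within half a point and only the beta is wrong. That stands: a reader might infer that the power is misstated or the trial too small, and the arithmetic does not support it.

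It can also be said that the plan does compare the groups. Section 9c i says so, the interaction is itself a comparison of arms, and a group effect is a natural output of such a model. This too stands, so it would be wrong to say that no group comparison is planned. What is absent is its test, time point and model term. Likewise, iib-10 names no time point; the single comparison is inferred from the formula. The 0.05 level applies to each subscale, but nothing says how the two results combine.

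The interaction figures rest on assumed correlations. One might infer that a benefit at 2 weeks only is exactly as detectable as one at all visits. That equality holds only under compound symmetry; at autoregressive correlation 0.5 the figures are 90% and 75%. The point that the interaction cannot separate the two patterns does not depend on it.

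Finally, a reader might conclude from the differing visit anchors that no single-visit contrast can be drawn from the text. The 2-week visit is clearly tied to the immediate reconstruction. For the primary outcome, Specific Aims, the Study Schema and iib-8 agree on "6 months and one year (+/- 1 month) following completion of reconstruction" or its equivalent. The competing statement, "The patient outcome data will be collected at months 6 and 12 months post-mastectomy by the Breast Q", belongs to the cost-effectiveness text, though it concerns the same questionnaire; the questionnaire timing table says only postop. The conflict therefore matters only if a 6- or 12-month contrast is chosen.

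**Conclusion.** The point holds in two parts. First, 85% power and beta 0.1 are incompatible; 72 per arm corresponds to beta 0.15, and the 85% and the sample size both stand if 85% was intended. If beta 0.1 was intended, 85 or 86 per arm would be needed. This part is certain for a two-sided test, and a one-sided reading does not remove the contradiction.

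Second, the 85% applies to one two-group comparison of one subscale, which the primary analysis leaves unspecified. It does not transfer to the named interaction, whose power ranges from about 63% to 99% over the assumed correlations and structures; that range is an illustration and not an estimate for this trial. No result of that test would by itself establish the hypothesis of benefit at all three visits, and the two subscales have no combining rule. The plan should be corrected, but nothing here shows that the trial is underpowered.

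**What to change.** 1. In iib-10, once the sponsor confirms that 85% was intended, state power 85% (beta 0.15), 72 evaluable per arm, for a single two-group comparison of one subscale.

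2. In 9c i, before comparative Breast Q data are examined, name the between-group difference as the primary test. Take it from a model of the post-operative scores with baseline Breast Q, site and laterality as covariates. Use either one chosen time point or planned contrasts at all three with a stated success rule; both close the gap. Keep the interaction as supportive. If a 6- or 12-month contrast is used, give it one anchor throughout Specific Aims, the Study Schema, the questionnaire timing table, iib-8 and 9c.

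3. State whether one or both subscales must be significant. If either suffices, use Holm or a fixed order. If both are required, no alpha adjustment is needed, but report the joint power of about 72% to 81% under the assumed correlations.

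**Cost.** No extra patients if 85% is confirmed, but a documented amendment in a trial already recruiting. The only interim analysis described covers short-term complications, so the documents report no comparative look at Breast Q. Choosing one time point narrows the primary claim. Under Holm, power falls from 85.1% to about 77.6% when only one subscale differs; a fixed order keeps 85% for the first subscale. Questionnaires already collected may need mapping to the chosen anchor.
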